3.6 Exclusion criteria

- presence of general danger signs in children aged under 5 years or signs of severe falciparum malaria according to the definitions of WHO (Appendix 1);
- Age less than 2 years old and over 60 for ASP, under 18 and over 60 for ASMQ;
- mixed or mono-infection with another *Plasmodium* species detected by microscopy;
- presence of severe malnutrition (defined as a child whose growth standard is below -3 z-score, has symmetrical oedema involving at least the feet or has a mid-upper arm circumference < 115 mm);
- presence of febrile conditions due to diseases other than malaria (e.g. measles, acute lower respiratory tract infection, severe diarrhea with dehydration) or other known underlying chronic or severe diseases (e.g. cardiac, renal and hepatic diseases, HIV/AIDS);
- regular medication, which may interfere with antimalarial pharmacokinetics;
- history of hypersensitivity reactions or contraindications to any of the medicine(s) being tested or used as alternative treatment(s);
- a positive pregnancy test or breastfeeding;
- unable to or unwilling to take pregnancy test or to use contraception for women of child-bearing age (defined as age > 12 years and sexually active).

3.7 Loss to follow-up

Loss to follow-up occurs when, despite all reasonable efforts, an enrolled patient does not attend the scheduled visits and cannot be found. No treatment outcome will be assigned to these patients. Every effort must be made to schedule a follow-up visit for patients who fail to

return to the study site, especially during but also after administration of the study drug. These patients will be classified as lost to follow-up and censored or excluded from the analysis. Patients who are lost to follow-up, but who subsequently return to the study site before day 42 for *P. falciparum* patients or before day 28 for *P. vivax* will not be turned away and will be encouraged to return for check-up visits. The principal investigator will decide whether the patient is to be definitely classified as lost to follow-up on the basis of his or her history or is to be maintained for the analysis.

3.8 Patient discontinuation or protocol violation

Study patients who meet any of the following criteria will be classified as withdrawn.

- withdrawal of consent. A patient may withdraw consent at any time, without prejudice for further follow-up or treatment at the study site.
- failure to complete treatment, due to:
 - persistent vomiting of the treatment. A patient who vomits the study medication twice will be withdrawn from the study and given rescue treatment.
 - failure to attend the scheduled visits during the first 3 days; or
 - serious adverse events necessitating termination of treatment before the full course is completed. A patient can be discontinued from the study if the principal investigator decides so due to an adverse event of adequate nature or intensity. In this case, information on the adverse event and symptomatic treatment given must be recorded on a case report form. If the adverse event is serious, the principal investigator must notify the sponsor or its designee immediately and follow the reporting procedures described in section 5.3.
- enrolment violation:
 - severe malaria on day 0; or
 - erroneous inclusion of a patient who does not meet the inclusion criteria.
- voluntary protocol violation: self- or third-party administration of antimalarial drug (or antibiotics with antimalarial activity) (Appendix 2);
- involuntary protocol violation:
 - occurrence during follow-up of concomitant disease that would interfere with a clear classification of the treatment outcome;
 - detection of mono-infection with another malaria species during follow-up; or
 - misclassification of a patient due to a laboratory error (parasitaemia), leading to administration of rescue treatment.

Patients who are withdrawn will nevertheless be followed up until recovery or the end of follow-up, if possible; however, no treatment outcome will be assigned to these patients, and they will be censored or excluded from the analysis. The reasons for discontinuation or protocol violation will be recorded on the case report form.

Pregnancy detected during the course of follow-up does not constitute a reason for withdrawal but the event must be recorded and managed as described in section 5.3.

4. TREATMENT

4.1 Antimalarial treatment

ASMQ (Artesunate + Mefloquine co formulated).

The adult dose tablet contains 100mg Artesunate plus 220mg Mefloquine and the paediatric tablet contain 55mg Artesunate plus 55 mg Mefloquine. (Refer to Annex table for more detailed dosage).

ASP (Artesunate + Pyronaridine/ Pyramax): Adults and children \geq 20 kg (Refer to Annex table for more detailed dosage).

All doses of medicine will be administered under the supervision of a qualified member of the staff designated by the principal investigator. The study patients will be observed for 30 min after medicine administration for adverse reactions or vomiting. Any patient who vomits during this observation period will be re-treated with the same dose of medicine and observed for an additional 30 min. If the patient vomits again, he or she will be withdrawn and offered rescue therapy. The patients are recommended to stay at the health facility until they complete the treatment course for malaria infection.

All doses of medicine will be administered under the supervision of a qualified member of the staff designated by the principal investigator. The study patients will be observed for 30 min after medicine administration for adverse reactions or vomiting. Any patient who vomits during this observation period will be re-treated with the same dose of medicine and observed for an additional 30 min. If the patient vomits again, he or she will be withdrawn and offered rescue therapy. The patients are recommended to stay at the health facility until they complete the treatment course for malaria infection.

4.2 Concomitant treatment and medication that should not be used

Fever over 38°C can be treated with paracetamol or acetaminophen. Parents or guardians will be instructed in the use of tepid sponging for children under 5 years of age.

Prior treatment with antimalarial drugs will not be considered an exclusion criterion; however, during follow-up, if infections other than malaria require the administration of medicines with antimalarial activity, the patient will be withdrawn from the study. Patients given tetracycline as an eye ointment will not be excluded (Appendix 2). Patients will be withdrawn from the study in the case of self-medication or if an antimalarial drug or an antibiotic with antimalarial activity is administered by a third party.

Adverse events requiring treatment can be treated according to local practice to the best available local practice. If there is a clinical indication for any additional medication during the course of the study, including medication given to treat an adverse event related to the study medicine, the name of the medicine, the dosage and the date and time of administration must be recorded on the case report form.

The use of herbal remedies during the study should be avoided, and participants should be encouraged to return to the study site for treatment if they feel unwell. If any herbal remedies

are taken during the study, this should be captured on the case report form, under 'study medication administration'.

4.3 Rescue treatment

If the patient vomits twice the treatment he/she will receive parenteral therapy based on national treatment guideline. If a patient is unable to tolerate the trial medication he/she should discontinue the treatment and alternative anti-malaria medication should be initiated. In this case, the reason for discontinuation should be recorded in the case record form (CRF) as "Adverse experience" and be withdrawn from the study.

Any patient with sign of severe malaria, will be hospitalized and receive parenteral therapy with artemether or quinine 7 days (IV) + tetracycline 7 days as well as relevant supportive treatments. If a patient meets one of the criteria for therapeutic failure, he/she will receive artemether at D1 3.2mg/kg (max 160mg) intramuscularly, D2 1.6 mg/kg (max 80mg) IM, from D3 to D5 1.6 mg/kg (max 80mg) per day IM and D6 plus mefloquine 25mg/kg spreading over 3 days (max 1250mg) according to the current national recommendations.

5. EVALUATION CRITERIA

The study end-point is the classification assigned to a patient. Valid study end-points include: treatment failure, completion of the follow-up period without treatment failure (adequate clinical and parasitological response), loss to follow-up, withdrawal from study, and protocol violation. At all times, the well-being of the patient will take priority over his or her continuation in the study.

5.1 Efficacy and safety evaluation

5.1.1 Classification of treatment outcomes

Treatment outcomes will be classified on the basis of an assessment of the parasitological and clinical outcome of antimalarial treatment according to the latest WHO guidelines.³ Thus, all patients will be classified as having early treatment failure, late clinical failure, late parasitological failure or an adequate clinical and parasitological response, as defined in Appendix 4.

As parasitological cure is the goal of antimalarial therapy, all study patients who show treatment failure will be given rescue treatment. Follow-up will continue until recovery. The results from these patients do not need to be recorded systematically for the purpose of the surveillance study.

5.1.2 Safety end-points

The incidence of any adverse event will be documented. All patients will be asked routinely about previous symptoms and about symptoms that have emerged since the previous follow-up visit. When clinically indicated, patients will be evaluated and treated appropriately. All adverse events will be recorded on the case report form. Serious adverse events (see definitions in 5.3) must be reported to the sponsor.

³ WHO. *Susceptibility of Plasmodium falciparum to antimalarial drugs. Report on global monitoring 1996–2004*. Geneva, World Health Organization, 2005 (WHO/HTM/MAL/2005.110) (<http://www.who.int/malaria/resistance>).

5.2 Clinical evaluation

All patients will be evaluated clinically as described below.

5.2.1 Physical examination

A standard physical examination will be performed at baseline (day 0 before dosing) and on days 1, 2, 3, 7, 14, 21, 28, 35 and 42. A complete medical history including prior and concomitant medication, demographic information and contact details will be taken at baseline.

5.2.2 Body weight

Body weight will be recorded on day 0 to the nearest kilogram on a Salter scale or on a hanging scale for young children. The scales will be properly calibrated. Patients should not wear excessive clothing while being weighed as this can overestimate their true weight. All young children should only wear undergarments while being weighed. The screening weight will be used to satisfy the inclusion or exclusion for nutrition status as well as to calculate the dose (number of tablets) to be administered. When assessing weight-for-height, children over 24 months of age should have their heights measured while standing. For simplicity, however, infants and children under 87 cm can be measured lying down (or supine) and those above 87 cm standing.

The reliability of the scales will be verified before the study begins and checked at regular intervals.

The circumference of the left mid-upper arm will be measured, at the mid-point between the elbow and the shoulder, and will be recorded to the nearest 0.2 cm. Oedema will be assessed by thumb pressure for 3 s on the dorsal surface of both feet.

5.2.3 Body temperature

Axillary temperature will be measured at baseline (day 0 before dosing) and on days 1, 2, 3, 7, 14, 21, 28, 35 and 42. Temperature will be measured with a thermometer that has a precision of 0.1 °C. Temperature will also be measured as clinically indicated. If the result is < 36.0 °C, the measurement will be repeated. The same route should be used throughout the study.

The quality of the temperature-taking technique and the thermometers should be assessed regularly. Thermometers should be tested in a water-bath of known temperature before the study begins and at regular intervals thereafter.

5.2.4 Microscopic blood examination

Thick and thin blood films for parasite counts should be obtained and examined at screening on day 0 to confirm adherence to the inclusion and exclusion criteria. Thick blood films will be also examined every 8 hours on days 1, 2, 3 and once on days 7, 14, 21, 28, 35 and 42 or on any other day if the patient returns spontaneously and parasitological reassessment is required. Specimens will be labeled anonymously (screening number or study number, day of follow-up, date). If this is a study to investigate parasitological response to a monotherapy with artemisinin-related compounds the number of parasite counts must be specified, e.g.: 2 thick blood films should be taken 12-hourly after screening for the 3 days or until parasite count is negative.

A fresh Giemsa stain dilution will be prepared at least once a day and possibly more often, depending on the number of slides to be processed. Giemsa-stained thick and thin blood films will be examined at a magnification of 1000 × to identify the parasite species and to determine the parasite density.

Three blood slides per patient will be obtained: two thick blood smears and one thin blood smear. One slide will then be stained rapidly (10% Giemsa for 10–15 min) for initial screening, while the others will be retained. If the patient is subsequently enrolled, the second slide will be stained more carefully (e.g. 2.5–3% Giemsa for 45–60 min), and slower staining will also be used for all slides obtained at follow-up visits. The study number of the patient, the date and the day of follow-up will be recorded either on the frosted edge of the slide or on the glass with a permanent glass pen.

The thick blood smear for initial screening will be used to count the numbers of asexual parasites and white blood cells in a limited number of microscopic fields. The adequate parasitaemia for enrolment is at least one parasite for every 16 white blood cells, corresponding to approximately 500 asexual parasites per microlitre for low-to-moderate transmission areas.

The second blood smear will be used to calculate the parasite density, by counting the number of asexual parasites in a set number of white blood cells (typically 200) with a hand tally counter. Once a field has been started, it must be counted to completion; the final number of white blood cells will therefore rarely be exactly 200. If more than 500 parasites have been counted before 200 white blood cells have been reached, the count will be stopped after the reading of the last field has been completed. Parasite density, expressed as the number of asexual parasites per µl of blood, will be calculated by dividing the number of asexual parasites by the number of white blood cells counted and then multiplying by an assumed white blood cell density (typically 6000 per µl).

$$\text{Parasite density (per } \mu\text{l)} = \text{number of parasites counted} \times 6000$$

$$\text{Number of leukocytes counted}$$

The same technique will be used to establish the parasite count on each subsequent blood film. When the number of asexual parasites is less than 100 per 200 white blood cells in follow-up smears, counting will be done against at least 500 white blood cells (i.e. to completion of the field in which the 500th white blood cell is counted).

A blood slide will be considered negative when examination of 1000 white blood cells or 100 fields containing at least 10 white blood cells per field reveals no asexual parasites. The presence of gametocytes on an enrolment or follow-up slide will be noted, but this information will not contribute to basic evaluation.

In addition, 100 fields of the second thick film at day 0 will be examined to exclude mixed infections; in case of any doubt, the thin film will be examined for confirmation. If examination of the thin film is not conclusive, the patient will be excluded from the analysis after complete treatment and follow-up.

Two qualified microscopists will read all the slides independently, and parasite densities will be calculated by averaging the two counts. Blood smears with discordant results (differences between the two microscopists in species diagnosis, in parasite density of > 50% or in the presence of parasites) will be re-examined by a third, independent microscopist, and parasite density will be calculated by averaging the two closest counts.

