3.5 Inclusion criteria

- For those receiving ASP: age between 2 and 60 years
- For those receiving ASMQ: age between 18 and 60 years;
- mono-infection with *P. falciparum* or *P. vivax* by microscopy; *P. falciparum* or *P. vivax* parasitaemia of 500-100,000/ μ l asexual forms;
- presence of axillary ≥ 37.5 °C or history of fever during the past 24 h;
- ability to swallow oral [by mouth] medication;
- ability and willingness to comply with the study protocol for the duration of the study and to comply with the study visit schedule; and
- informed consent from the patient or from a parent or guardian in the case of children aged less than 12 years;
- informed assent from any minor participant aged more than 12 years and less than 60 years; and
- consent for pregnancy testing from female of child-bearing potential and from their parent or guardian if under 18 years.

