APPENDIX 5. CASE SCREENING FORM

Case screening form	
Health centre name:	Study number:
Locality:	Patient screening number:
District:	Date of visit (dd-mm-yyyy):
Province:	
Demographic data	
Date of birth (dd-mm-yyyy):	or estimated age: in:  months or  years
Height (cm):	Weight (kg):
Sex:  Male  Female	
If female, is the patient pregnant?  Yes  No  Not sure (If yes, patient is not eligible)	
If pregnant, provide the date of the last menstrual period (dd-mm-yyyy):	
Pre-treatment temperature	
History of fever in previous 24 h?  Yes  No	
Temperature: °C  Axillary	
Thick and thin blood smears for estimation of P. falciparum parasite counts	
Species:  P. falciparum  P. vivax  P. ovale  P. malariae	
Were species other than P. falciparum present?  Yes  No (If yes, patient is not eligible).	
Approximate number of P. falciparum asexual parasites:	
Presence of 1–200 parasites / 12 white blood cells?  Yes  No (If no, patient is not eligible)	
Presence of P. falciparum gametocytes?  Yes  No	
Has a blood sample for PCR been collected?  Yes  No	
Haematocrit: %	
Urinary analysis (pregnancy test for female patients)	
Result of pregnancy test:  Positive  Negative (If positive, patient is not eligible)	
Inclusion criteria	

 • age between 2 and 60 years • mono-infection with P. falciparum confirmed by positive blood smear (i.e. no mixed infection) • parasitaemia between 500 and 100,000/μl of asexual forms • measured temperature (depending on method of measurement) or history of fever within previous 24 h • ability to swallow medication 	

 • ability and willingness to comply with the study protocol for the duration of the study and to comply with the study visit schedule • absence of severe malnutrition (defined as per protocol) 	

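### The enrolment ratio of 1 parasite per 16 white cells in section 5.2.4 works out at 375/µl by the protocol's own formula, not the stated 500/µl, and conflicts with the screening form

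*Protocol*

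**What the plan says.** Four places in the protocol bear on the lower parasitaemia limit.

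- **Section 3.5 (inclusion criteria)** requires "parasitaemia of 500-100,000" asexual forms per µl, for either species.
- **Section 5.2.4, screening slide:** "The adequate parasitaemia for enrolment is at least one parasite for every 16 white blood cells, corresponding to approximately 500 asexual parasites per microlitre". This reading uses a rapidly stained slide and a limited number of fields.
- **Section 5.2.4, second slide:** once the patient is enrolled, a more carefully stained slide gives the recorded density. Parasites are divided by white cells counted, then the method is "multiplying by an assumed white blood cell density (typically 6000 per µl". The displayed formula also uses 6000.
- **Appendix 5 (case screening form)** asks whether there are 1 to 200 "parasites / 12 white blood cells" and makes the patient ineligible if not. It separately lists 500 to 100,000/µl as an inclusion criterion.

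Section 3.8 lists "erroneous inclusion of a patient who does not meet the inclusion criteria" among the enrolment violations. Such patients are classed as withdrawn, receive no treatment outcome, and are censored or excluded.

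**The concern.** A ratio of parasites to white cells becomes a density only through an assumed white-cell density. The protocol fixes that at 6000/µl, and the ratio in 5.2.4 does not then give the density printed beside it. The form used at screening carries a different ratio. One slide with a parasite for every 13 to 16 white cells is therefore adequate under 5.2.4 and ineligible under Appendix 5.

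At stake is a uniform entry threshold across five sites. If 5.2.4 is the rule applied at the bench, some patients can be treated and then recorded below the limit in section 3.5. If they are handled as erroneous inclusions, they drop out of the per-protocol proportion. In the Kaplan-Meier analysis they contribute almost nothing, because the analysis guidelines censor at the last scheduled day before the violation, and this violation dates from day 0. Section 8.1 leaves 60 − 54 = 6 patients per species and site for all losses.

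**Working it through.** **Inputs, all from the protocol:** ratio 1/16 and stated equivalent of about 500/µl (5.2.4); white-cell density 6000/µl (5.2.4); ratio 1–200 per 12 (Appendix 5); inclusion range 500–100,000/µl (3.5).

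**Formula (5.2.4):** density = parasites ÷ white cells × assumed white cells per µl.

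**Step 1. Try to reproduce the stated 500/µl.** 1/16 × 6000 = 375/µl. It is not reproduced. The shortfall is (500 − 375)/500 = 25%, too large for an approximation.

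**Step 2. Compare both ratios at both candidate densities.** The value 8000 is not in the document; it is what 1 per 16 needs to equal 500 (500 × 16 = 8000).

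| White cells/µl | 1 per 16 | 1 per 12 | 200 per 12 |
|---|---|---|---|
| 6000 | 375 | 500 | 100,000 |
| 8000 | 500 | 667 | 133,333 |

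No single density makes both ratios correct. At 6000 the form reproduces both limits of section 3.5 exactly. The formula, the form and the criterion agree with one another; only the 16 does not fit.

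**Step 3. The same gap on the second slide.** Against 200 white cells at 6000/µl, 500/µl corresponds to 500 × 200/6000 = 16.7 parasites. The 5.2.4 ratio admits from 200/16 = 12.5.

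**Step 4. How many patients could lie at 375–499/µl?** The documents give no baseline density distribution, so this is illustration only. If densities were spread evenly on a log scale from 375 to 100,000/µl (assumption), the band would hold ln(500/375)/ln(100,000/375) = 0.288/5.586 = 5.2%, or about 3 of 60. If every site applies the form, the number is 0.

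**Step 5. Effect on precision.** With the section 8.1 inputs (failure 10%, 95% confidence), half-width = 1.96 × √(0.1 × 0.9/n):

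- n = 54: 8.0 points, the planned precision
- n = 51 (all 6 planned losses plus 3 more): 8.2 points
- n = 48 (plus 6 more): 8.5 points

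The 3 and 6 extra losses are illustrative assumptions.

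**The case against.** The strongest reply is that the form prevents the harm. Section 6.1 makes Appendix 5 the screening record and allows enrolment only when all criteria are met. A patient at 375–499/µl fails the form twice: on the ratio and on the listed 500/µl limit. This largely stands. A reader might infer from the faulty ratio that ineligible patients are being enrolled and later removed, using up much of the 10% allowance. The documents do not support that, for three reasons.

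- It requires staff to follow 5.2.4 over the form.
- Removal after the second slide is an inference from section 3.8. The only explicit exclusion that 5.2.4 attaches to the second-slide examination concerns unresolved mixed infection; it has none for a density recalculated below 500/µl.
- The documents give no figure for the share of patients in the band.

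The form is not a complete safeguard, however. Its slide section is worded for *P. falciparum*, and it declares a patient ineligible if another species is present. It therefore does not fit the *P. vivax* patients, who are 60 of the 120 planned per site.

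A second reply is that the screening count is coarse: 5.2.4 tolerates differences of up to 50% between two readers before a third reading. That is also fair. Treating one reader's count against 200 white cells as Poisson (assumption), a patient truly at 500/µl reads below 500 about 50% of the time, and one at 600/µl about 22%. Correcting the ratio will not end borderline disagreements. It removes a systematic 25% offset, which random counting error does not excuse.

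**Conclusion.** The inconsistency is certain. By the protocol's own formula the ratio in 5.2.4 gives 375/µl, 25% below the density it is said to represent, and it contradicts the ratio on the screening form. This rests only on the 6000/µl that the protocol prescribes.

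The consequence is conditional. Patients at 375–499/µl can be enrolled where 5.2.4 is followed instead of the form, and may then be treated as erroneous inclusions. How many cannot be estimated from the documents, and it may be none. Even 6 further losses in a stratum, on top of all planned losses, would widen the half-width by only about 0.5 percentage points, and nothing here shows bias in the efficacy estimate. This is a clear error worth correcting, but of low priority.

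**What to change.** In section 5.2.4, and in any microscopy bench aid drawn from it, change the 16 to 12. The screening text, the 6000/µl formula, the limit in section 3.5 and Appendix 5 then give one threshold. Nobody's eligibility under section 3.5 changes.

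Keeping 16 would be coherent only with 8000 white cells/µl in the density formula and a form rewritten as 1 to 200 per 16. That is more editing, and it brings in a density the protocol does not use.

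The cost is one number in the protocol, the matching bench aid, and the agreement that section 8.4 requires for any change.
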